While these studies documented the importance of HE, and that it is more frequent and severe the earlier it is sought, no studies to date have evaluated HE in the first 1-2 hours after onset of ICH. Extrapolating from clinical data described above, it is very likely that HE will be even more frequent during the first hour after bleeding starts, and that interventions to limit bleeding might be most effective during this time interval. The advent of the Mobile Stroke Unit (MSU) where patients are evaluated and imaged within the first hour after onset of symptoms will make it possible for the first time to examine the natural history of this early hematoma enlargement (EHE), the use of TEG as a predictor of EHE, and the effect of interventions to limit it.

Aim 1: Use the MSU platform to evaluate the natural history of EHE

- 1a. We hypothesize that significantly more EHE will occur in the first two hours after symptom onset compared to later.
 - 1a.i. The number of patients with EHE will be more.
 - 1a.ii. The volume of EHE will be more.

All patients with ICH scanned on the MSU will have a repeat CT 1 hour after the initial CT. We will determine the number of patients with EHE, and the average volume of EHE, in patients scanned within the first 2 hours (and in the 0-1 hour and 1-2 hour groups separately), and compare results to those scanned 2-4 hours after onset.

1b. We hypothesize that there will be significantly smaller hematoma volume in patients having initial scan within 2 hours of symptom onset compared to those scanned 2-4 hours either on the MSU or in the ED.

Patients will be included if they have baseline CT carried out within 4 hours of symptom onset, whether initially scanned on the MSU or in the ED. The difference in average volume between those with baseline scan within 2 hours of symptom onset vs those scanned 2- 4 hours after onset will represent the average volume of EHE occurring during the time interval between the two populations (The 0-2 hour group will be analyzed as a whole, and also the 0-1 and 1-2 hour groups separately).

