- 1. Primary or predominant IVH, SAH, or SDH
- 2. IVH with filling of >50% of the lateral ventricle

Interventions:

Group 1: Patients transported on the MSU found to have ICH on CT will receive protocolized BP treatment with Nicardipine or Labetalol to reduce SBP to 140-150 mm Hg in the MSU before arrival to ED (and treatment with 4F-PCC, if INR > 1.4, or Praxbind, if Dabigatran is used within the prior 48 hours).

Group 2: Patients in the SM arm of the MSU study (no MSU deployment) later found to have ICH after CT in the ED will receive pre-hospital treatment as per EMS routine (control of SBP to no lower than 180 mm Hg using labetalol) followed by standard management of BP, elevated INR, or Dabigatran usein ED

Primary Outcomes (All hematoma volumes measured by the AXBXC/2 method):

Aim 1:

- 1. Incidence of hematoma expansion(defined as increase in hematoma size by > 6cc or by 30%) and volume of EHE (ICH volume on 1 hour follow up scan ICH volume on initial CT) in Group 1 patients who had initial CT scan within 4 hours of onset. 'EHE' will be used to indicate hematoma expansion occurring in patients captured within 2 hours from onset and 'HE' will be used to indicate hematoma expansion that is captured later. We will analyze the entire group of patients scanned within 2 hours as a whole, and also those scanned within 1 hour and between 1-2 hours separately, and compare with those scanned later. We will evaluate coagulopathic and non-coagulopathic related ICH patients separately.
- 2. Difference in average hematoma volume on baseline scans between 0-2 hour and 2-4 hour patients (Group 1 or 2). We will analyze the entire group of patients scanned within 2 hours as a whole, and also those scanned within 1 hour and between 1-2 hours separately, and compare with those scanned later. The difference in average volume will represent the average volume of EHE occurring during the time interval between the two populations. We will evaluate coagulopathic, and non-coagulopathic related ICH patients separately.

Aim 2:

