Aim 1a. If we assume a 30% incidence of HE in the 2-4 hour group, and expect an increase to 60% in the 0-2 hour group, a total of 94 patients (47 per group) adjusting for multivariable analyses will be needed to achieve 80% power to detect this difference with a 0.05 two sided significance value.

Aim 1b. Based on previous studies, the mean \pm SD of the logarithmic hematoma volume in the 2-4 hour group should be 2.9 \pm 1.2. If we expect 30% smaller baseline hematoma volumes in the 0-2 hour group log vol = 2.0), to achieve 80% power, a total of 64 patients (32 per group) adjusting for multivariable analyses will be needed to achieve 80% power to detect this difference with a 0.05 two sided significance value.

Aim 2a. The expected incidence of EHE/HE and volume of hematoma growth will be derived from patients who present within 4 hours of onset (separated into 0-2 hour and 2-4 hour groups) who do not receive acute BP treatment or coagulopathy reversal. If we assume a 60% incidence of EHE in the 0-2 hour group and expect early BP treatment (or coagulopathy reversal) to reduce this to 30%, a total of 94 patients (47 per group) adjusting for multivariable analyses will be needed to achieve 80% power to detect this difference with a 0.05 two sided significance value.

Aim 3. We have previously studied TEG values in ICH patients presenting within 6 hours of onset and compared TEG values for those who developed HE to those who did not. K, which represents speed of clot formation, was significantly slower in patients with HE, with a mean difference of 1.5 ± 3.1 min. Assuming mean K in the 2-4 hour group will be 1.5 min longer than the 0-2 group and that there will be a 1.5 min difference between HE and non -HE patients, then we would expect a 3 min difference between the 0-2 hour EHE patients and the 2-4 hour non-HE patients. A total of 40 patients (20 in each group) adjusting for multivariable analyses will be needed to achieve 80% power to detect this difference with a 0.05 two sided significance value.

Procedures:

- Get baseline MSU CT loaded onto PACS for measurement.
- 2. Obtain careful documentation of BP and BP treatment X first 2 hours Group 1 and up to time of first CT scan in Group 2.
- 3. Obtain accurate history of previous meds, comorbidities, coags, baseline NIHSS.
- 4. Obtain TEG in all Group 1 pts.
- 5. Obtain 1 hr f/u CT and NIHSS in all Group 1 patients.
- 6. Obtain 24hr CT and NIHSS in all pts.

References:

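### ICH substudy Aim 1a is labelled natural history, but early haematoma growth is measured across protocolized MSU treatment that the comparison and its power statement ignore

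*Protocol*

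**What the plan says.** All references are to protocol Appendix 4 unless stated.

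- **Purpose.** Aim 1 is to "Use the MSU platform to evaluate the natural history of EHE". Aim 1a hypothesizes more enlargement, in number of patients and in volume, in the first two hours than later.
- **Measurement.** "All patients with ICH scanned on the MSU will have a repeat CT 1 hour after the initial CT". Under Primary Outcomes, the Aim 1 growth outcome is taken "in Group 1 patients who had initial CT scan within 4 hours of onset", and patients scanned within 2 hours are compared with those scanned later.
- **What Group 1 receives.** Under Interventions, MSU patients found to have ICH "will receive protocolized BP treatment with Nicardipine or Labetalol to reduce SBP to 140-150 mm Hg in the MSU before arrival to ED", plus 4F-PCC if INR exceeds 1.4 or Praxbind if dabigatran was used in the prior 48 hours.
- **Adjustment.** The Sample Size heading lists baseline NIHSS, antiplatelet use and comorbidities for all analyses. Treatment between the scans is not listed. The only split planned for the Aim 1 outcomes, apart from time, is coagulopathic versus non-coagulopathic ICH.
- **Sizing of Aim 1a.** The plan sets a 30% rate of enlargement at 2-4 hours against 60% at 0-2 hours, giving 94 patients (47 per group) for 80% power at two-sided 0.05, with an allowance for multivariable analysis.
- **Sizing of Aim 2a.** Expected rates come from patients without acute treatment. The plan assumes "a 60% incidence of EHE in the 0-2 hour group and expect early BP treatment (or coagulopathy reversal) to reduce this to 30" per cent, again with 47 per group.

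**The concern.** A natural-history estimate needs growth that treatment has not altered. In Group 1, ICH on the first CT triggers treatment, which is given before ED arrival. It therefore starts after scan one. It should normally precede scan two: protocol section 4.C reports a mean on-scene time of 28 minutes (range 12-53) in the run-in, although transit time is not given.

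The substudy's own hypothesis is that this treatment prevents enlargement. If so, the Aim 1a event rates are lowered to an unknown extent, and the excess of early growth that Aim 1a is meant to detect shrinks. A null result could then be read as showing that growth is no more frequent in the first two hours. A positive result would understate the untreated difference. The stated 80% power also rests on a 60% early rate that a partly treated group may not have.

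**Working it through.** **Inputs.** From Aim 1a: 60% (0-2 h), 30% (2-4 h), two-sided 0.05, 80% power, 47 per group. From Aim 2a: 60% without treatment and 30% with it in the 0-2 h group, a halving of incidence. Not in the documents: the share *t* of Group 1 treated between the scans, and whether the halving applies to the 2-4 h window. Both are varied below.

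**Step 1: reproduce the plan's figure.** With the pooled-variance formula for two proportions,

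n = [1.96·√(2p̄q̄) + 0.842·√(p₁q₁ + p₂q₂)]² / (p₁ − p₂)²

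and p₁ = 0.60, p₂ = 0.30, p̄ = 0.45:

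n = [1.96·√0.495 + 0.842·√0.45]² / 0.09 = (1.379 + 0.565)² / 0.09 ≈ 42 per group.

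The plan gives no factor for its multivariable allowance. An assumed 10% gives 42/0.9 = 46.7, rounded up to 47 per group and 94 in total, which matches. The 80% thus belongs to 42 per group.

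**Step 2: unadjusted power at 47 per group.**

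Power = Φ{[(p₁ − p₂)·√47 − 1.96·√(2p̄q̄)] / √(p₁q₁ + p₂q₂)}

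With nobody treated: (0.30 × 6.856 − 1.379) / 0.671 = 1.01, so power is 84%. This is the like-for-like starting point.

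**Step 3: let a share *t* be treated.**

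- Scenario A, halving in both windows: 0-2 h rate = 0.60(1 − 0.5t); 2-4 h rate = 0.30(1 − 0.5t).
- Scenario B, halving only in the 0-2 h window, the one for which Aim 2a states it: 2-4 h rate stays 0.30.

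| Share treated | A: rates (0-2 h vs 2-4 h) | A: power | B: rates (0-2 h vs 2-4 h) | B: power |
|---|---|---|---|---|
| 0% | 60% vs 30% | 84% | 60% vs 30% | 84% |
| 25% | 52.5% vs 26.3% | 75% | 52.5% vs 30% | 60% |
| 50% | 45% vs 22.5% | 64% | 45% vs 30% | 32% |
| 75% | 37.5% vs 18.8% | 53% | 37.5% vs 30% | 12% |
| 100% | 30% vs 15% | 41% | 30% vs 30% | 5% |

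The last entry under B is simply the significance level, since no difference remains. With the same 10% allowance, scenario A would need 120, 154, 200 and 270 patients in total at 25%, 50%, 75% and 100% treated, against the planned 94.

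**The case against.** The strongest reply is that Aims 1a and 2a do not describe the same quantity. Aim 2 is limited to patients with a systolic reading above 150, INR above 1.4 or recent dabigatran use; Aim 1 has no such limit. Aim 2 counts enlargement from baseline to 24 hours; Aim 1a counts it at one hour. Aim 1a's 60% is not itself labelled as an untreated rate. A reader might infer that the two sets of rates cannot both hold in the same patients. The documents do not show that, because population and endpoint both differ. The halving is carried over to the one-hour scan here as an illustration only.

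Nor do the documents support reading every Group 1 patient as treated, or growth itself as halved. Treatment follows an indication, so patients with neither raised pressure nor coagulopathy would probably go untreated and dilution is partial. Aim 2a quantifies the number of patients with enlargement, not volume.

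The plan also goes part of the way. Aim 2 draws its expected rates from untreated Aim 1 patients, so it presumes that such a subset can be identified, and the coagulopathy split largely separates those given reversal. Scenario A is arguably more plausible than B, since both windows lie in Group 1 under one treatment protocol.

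These points limit the size of the effect. They do not answer the core observation: Aim 1a is not defined on the untreated subset, blood-pressure treatment is not separated out, and the power statement carries no condition.

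**Conclusion.** The point stands as a mismatch between label and measurement within Appendix 4. Aim 1a as written estimates early enlargement under MSU management, not natural history, and its 80% power holds only if treatment between the scans does not reduce growth.

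The size cannot be fixed from the documents. Using Aim 2a's own halving, power at 47 per group lies between 84% and 41% if treatment acts in both windows, and falls as low as 5% if it acts only in the first. Both ranges assume that the one-hour effect equals the effect assumed for 24 hours. Scenario A also assumes the same treated share in both windows.

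In both scenarios the contrast shrinks, so it is chiefly a null result that becomes uninterpretable; a positive one would remain credible. The main trial's primary outcome is not affected.

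A reader might also infer that Aim 1b, which uses baseline scans only, gives a treatment-free natural history. That goes too far. Protocol section 5.C.3 has the MSU team controlling blood pressure as needed before the CT, and Group 2 patients may receive labetalol from EMS before their ED scan.

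**What to change.** 1. Describe Aim 1a as early growth under MSU management rather than natural history.
2. Report the 0-2 h versus 2-4 h comparison separately by whether blood-pressure treatment or reversal began before the one-hour scan. The untreated subset is already presumed by Aim 2, and the needed times (CT, first blood-pressure treatment, reversal) are on the list of variables to be measured. State beside the table that treated and untreated patients differ by indication, so the split is descriptive.
3. State that the 80% power for Aim 1a holds only if growth is not reduced by treatment between the scans.

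Two other remedies should be avoided. Adjusting for time from first CT to treatment would condition on a post-baseline variable that is undefined in untreated patients. Moving the natural-history claim to Aim 1b as if its scans preceded all treatment would repeat the problem in milder form.

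The cost is some rewording of Appendix 4, one extra stratified table with strata smaller than the planned groups, and a less favourable power statement. No new data are needed and care does not change.

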Rationale —HE is associated with worse outcome after either hypertensive or coagulopathic ICH. Most HE occurs within the first few hours after onset (see summary of literature above), but is probably grossly underestimated since patients are rarely seen and scanned within the first hour or so after onset when HE is most likely to occur. Early hematoma enlargement (EHE) occurring in the first 1-2 hours after bleeding onset may be much more frequent, proportionately larger in volume, and have a more important effect on outcome than HE during the ensuing hours. However, knowledge about EHE is limited as it is very rare to capture patients in this hyperacute period. MSU management will allow us for the first time to asses EHE.

Aim 2: Investigate the effect of early blood pressure (BP) control or coagulation reversal in ICH patients on EHE. Patients with at least one SBP reading >150, INR > 1.4, or use of Dabigatran within the prior 48 hours will be included in this Aim.

- 2a. We hypothesize that BP treatment (or coagulopathy reversal) within the first 2 hours after onset, as facilitated by the MSU, will reduce the number of patients having EHE.
- 2b. We hypothesize that BP treatment (or coagulopathy reversal) within the first 2 hours after onset, as facilitated by the MSU, will reduce the volume of EHE.

Patients will be included if they have baseline CT carried out within 4 hours of symptom onset, whether initially scanned on the MSU or in the ED. We will compare the number of patients who

develop EHE and change in hematoma volume from baseline to 24 hours in patients having BP treatment (or coagulopathy reversal) begun within the first 2 hours after symptom onset (the 0-2 hour group will be analyzed as a whole, and also the 0-1 and 1-2 hour groups separately) to what is expected. Similarly, we will compare the same outcomes for those treated in the 2-4 hour group to the expected number of patients with EHE and expected change in hematoma volume. The expected incidence of EHE and amount of hematoma growth will be calculated based on what is observed from the untreated patients in SA1 and compared to their respective 0-2 hour or 2-4 hour group. The difference in number of patients with EHE, and in average volume, will represent the number of patients with EHE and the average volume of EHE prevented by earlier management. The proportion of patients in the 0-2 hour and 2-4 hour group treated in the MSU versus ED will be calculated.

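### Appendix 4, Aim 2: the expected expansion rate comes from untreated patients who would mostly lack an Aim 2 entry trigger, and the scan that supplies it is not stated, so the difference cannot be read as expansion prevented

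*Protocol*

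**What the plan says.** All references are to Protocol Appendix 4 unless stated.

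- **Entry to Aim 2.** The Aim is open to "Patients with at least one SBP reading >150, INR > 1.4, or use of Dabigatran"; dabigatran counts if it was taken in the preceding 48 hours.
- **Treatment, Group 1 (MSU).** ICH patients "will receive protocolized BP treatment with Nicardipine or Labetalol to reduce SBP to 140-150 mm Hg in the MSU before arrival to ED", and the same sentence adds "treatment with 4F-PCC, if INR > 1.4, or Praxbind, if Dabigatran is used within the prior 48 hours".
- **Treatment, Group 2 (SM).** EMS routine, then standard ED management. The Aim 2 rationale describes that management as lowering systolic pressure, or giving a reversal agent, once CT confirms ICH.
- **Comparator.** The Aim 2 text says the expected incidence and growth "will be calculated based on what is observed from the untreated patients in SA1". The sample size text for Aim 2a words it more broadly: patients presenting within 4 hours "who do not receive acute BP treatment or coagulopathy reversal".
- **Scans.** The Aim 1 growth outcome is the change to a 1-hour follow-up scan, in Group 1 only. The Aim 2 volume outcome is the change from baseline to 24 (+12) hours, in Group 1 or 2. Under Procedures: "Obtain 24hr CT and NIHSS in all pts".
- **Adjustment.** Baseline NIHSS, antiplatelet use and comorbidities.
- **Interpretation.** Both the Aim 2 text and the Aim 2 outcome definition take the difference from expected as the expansion prevented by earlier management.

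**The concern.** A comparison with an expected rate supports a statement about prevention only if that rate is what the treated patients would have shown without treatment. Here the conditions that lead to treatment are close to the conditions that admit a patient to Aim 2. The untreated patients would therefore tend to be those with lower pressure and no coagulopathy, and the treated patients the opposite. If pressure or coagulation status affects expansion, which is the premise of Aim 2, the difference mixes the effect of treatment with the difference between the two kinds of patient.

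The scan time is a second, separate problem. Expansion accumulates, so a rate observed at 1 hour is not the right yardstick for growth to 24 hours. The appendix does not say which scan the expected value comes from.

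At stake is a causal conclusion about very early blood pressure treatment and reversal that could be wrong in size and possibly in sign.

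**Working it through.** **1. Entry criteria against treatment triggers.**

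| Condition | Admits to Aim 2 | Leads to treatment on the MSU |
|---|---|---|
| Systolic pressure | at least one reading >150 | lowered to 140-150 (no starting threshold stated) |
| INR | >1.4 | >1.4 |
| Dabigatran | within 48 hours | within 48 hours |

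The INR and dabigatran conditions are identical. For pressure, I infer from the upper end of the target that patients above 150 are treated. Taken literally, with no threshold, every Group 1 ICH patient would be treated and there would be no untreated Group 1 patients at all. SM patients are also treated, later, in the ED. On either reading, a patient managed as written and left untreated would mostly be one without an Aim 2 trigger.

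**2. The plan's own figure.** Aim 2a assumes 60% against 30%, two-sided 0.05, 80% power, and states 94 patients (47 per group).

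n per group = [1.96·√(2p̄(1−p̄)) + 0.8416·√(p₁(1−p₁)+p₂(1−p₂))]² / (p₁−p₂)², with p̄ = 0.45:

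[1.96·√0.495 + 0.8416·√0.45]² / 0.09 = 42, so 84 in total.

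84/0.90 = 93.3, rounded up to 94. The stated number is reproduced if the unspecified allowance for multivariable analysis is 10% (my assumption). Power at 47 per group:

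Φ[(√47·0.30 − 1.96·√0.495)/√0.45] = Φ(1.01) = 84%. (An exact Fisher test gives 79%.)

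**3. If the expected value were the 1-hour rate.** The background section cites a study with enlargement in 26% at 1 hour and a further 12% by 20 hours, so 38% in total. The ratio is 26/38 = 0.684. Assume that this ratio carries over and that 60% is the untreated rate at 24 hours.

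- Expected rate at 1 hour: 0.60 × 0.684 = 41.1%.
- Apparent benefit against 30% treated: 11.1 points instead of 30.
- Power at 47 per group: Φ[(√47·0.1105 − 1.96·0.677)/0.672] = Φ(−0.85) = about 20%. About 294 per group would be needed for 80%.
- With no treatment effect (38% in both groups at 20 hours): 26 − 38 = −12 points, an apparent harm.

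Aim 2a uses the same 60% that Aim 1a assumes for its 0-2 hour group, and Aim 1a rests on the 1-hour scan. This makes the 1-hour reading natural, but does not establish it.

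**4. The population difference.** The documents give no expansion rate for untreated patients without an Aim 2 trigger, so the rates below are assumptions. The true untreated rate in eligible patients is held at 60% and the treated rate at 30%.

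| Assumed rate in the untreated source | Apparent benefit (true: 30 points) | Power at 47 per group |
|---|---|---|
| 70% | 40 points | not computed |
| 60% | 30 points | 84% |
| 50% | 20 points | 51% |
| 40% | 10 points | 17% |
| 30% | 0 points | 5% |

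The error can go either way. If treatment did nothing (60% in treated patients), an untreated source at 40% would show 20 points of false harm, and one at 70% would show 10 points of false benefit.

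**The case against.** **Some overlap is possible.** A reader might infer that no untreated patient can meet Aim 2 entry. The documents do not support that. One reading above 150 is enough for entry, so a patient whose pressure settles, or whose treatment is missed, can be eligible and untreated. The sample size wording is not confined to Group 1, and Aim 1b also includes patients first scanned in the ED. This stands. Such patients would, however, be few and selected by the very course that spared them treatment, so they make a weak control group.

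**The scan mismatch is not a stated rule.** A reader might infer that the plan sets 1-hour growth against 24-hour growth. No text says so, and a 24-hour CT is planned for every patient, so a like-for-like value is available. This stands: the defect is that the source scan is unspecified.

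**The direction is open.** The study that supplies the 26% and 12% found no predictors of enlargement, and it examined blood pressure and prothrombin time. An assumed lower rate in low-pressure patients therefore has no support there. This stands against any one-sided estimate of the population bias. It does not make the groups exchangeable, and Aim 2 itself presupposes that pressure and coagulation matter.

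**Adjustment and stratification are planned.** The list of variables to be measured puts chronic hypertension and coagulopathy beside comorbidities, and Aim 1 analyzes coagulopathic ICH separately. This helps in part. Acute systolic pressure, INR and anticoagulant use are not named as covariates, and adjustment cannot do much where the groups hardly overlap.

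**Conclusion.** The concern holds in this form: the comparator is poorly exchangeable with the treated group, the scan behind the expected value is unspecified, and the reading of the difference as expansion prevented is unsupported.

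The only size that can be tied to figures in the documents is that of the timing problem: about 41% in place of 60%, about 11 points in place of 30, and power of about 20% in place of 84%. It applies only if the 1-hour scan is used. It assumes that the cited 26/38 ratio carries over to this population and to the appendix's own definition of expansion (more than 6 cc or 30%, where the cited study used more than 33%). That error would work against finding a benefit. The size and direction of the population bias cannot be determined from the documents.

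It would go too far to conclude that Aim 2 is bound to give a wrong answer, or that it is tilted in favor of the MSU. Neither follows from the text. The issue is confined to a substudy in an appendix; the primary uw-mRS comparison in tPA-eligible patients is untouched.

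**What to change.** 1. **Comparator and scan.** Restrict any comparator to patients who meet the Aim 2 entry criteria, and state that the 24-hour scan is used in both groups, for incidence as well as volume.
2. **Wording.** Label the comparison with the expected value as descriptive. Remove the statement that the difference represents expansion prevented by earlier management, in both the Aim 2 text and the Aim 2 outcome definition.
3. **Allocated comparison.** Add MSU versus SM in ICH patients meeting the Aim 2 criteria, with log 24-hour hematoma volume as outcome. Adjust for enrollment NIHSS, first systolic pressure, INR or anticoagulant use, and onset-to-enrollment time. Take the systolic reading that decides eligibility from a window recorded in both arms, because pressure is documented for 2 hours in Group 1 but only up to the first CT in Group 2. Add a sensitivity analysis without the 60 cc limit if volumes above it are recorded.
4. **Reconcile** inclusion item 3 with the Aim 2 text: the item omits dabigatran, while the text includes it.

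**Cost.** Mainly analysis wording in Appendix 4. Step 1 may leave few untreated patients, which is a further reason to keep that comparison descriptive. Step 3 answers a different question: the effect of MSU deployment rather than of treatment time. Its power is not established, and ED treatment of SM patients would narrow the contrast. Selection on the first CT remains a limitation, since the 60 cc and intraventricular limits apply at an earlier scan on the MSU. Enrollment NIHSS may also not be at the same stage in both arms, because under Section 5.C.4 the study team may first meet an SM patient in the ED.

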Rationale --BP lowering is currently being tested to prevent HE after hypertensive ICH, and drugs are now available (4 Factor Prothrombin Complex Concentrate-4F-PCC and Praxbind) to rapidly reverse the coagulopathy caused by warfarin (4F-PCC) or by other newer oral anticoagulants like Dabigatran (Praxbind). Current standard management is to lower the SBP in our ED to 130-150 mm Hg or to give 4F-PCC (for elevated INR) or Praxbind (when the concurrent use of Dabigatran is suspected) once ICH is confirmed on CT scan. In both the aggressive and standard treatment arms of ATACH, patients will probably receive lowering of SBP to about 150 mm Hg (and lower in the aggressive treatment arm) after arrival to the ED. However, therapy begun in the ED will not result in BP lowering (or coagulopathy reversal) within the first hour of onset, and rarely within the first 2 hours. MSU management will permit such early BP lowering (or coagulopathy reversal) and allow us to assess its results on preventing EHE.

Aim 3: Determine if coagulation status, as measured by thromboelastography (TEG), is more altered very early after the onset of spontaneous (non-coagulopathic) ICH compared to later, and if TEG predicts EHE.

- 3a. We hypothesize that the pro-coagulation response to ICH will be greater soon after the onset of bleeding.
- 3b. We hypothesize that patients without early pro-coagulation changes on TEG will be more likely to develop EHE.

We will compare TEG values in MSU patients studied within the first 2 hours after symptom onset to those studied later, and in patients with EHE to those without. Patients with bleeding due to known coagulopathy or antithrombotic therapy will be excluded from this Aim.

Rationale -- We have shown that ICH is associated with faster and stronger clot formation as measured by TEG, but that patients with HE do not demonstrate this presumably adaptive response to bleeding. It is possible that failure to mount this hypercoaguable state after ICH may be important in leading to HE. This dynamic has never been studied in the first hours after ICH onset when EHE may be more frequent and dramatic than later HE. MSU management will allow us to obtain TEG measurements in the first hours after ICH onset and correlate them with EHE.

Inclusion Criteria:

- 1. Enrollment into MSU study (meeting all inclusion criteria)
- 2. Parenchymal ICH on first CT scan < 60cc
- 3. At least one SBP reading >150 or INR > 1.4 (only for SA 2)

Exclusion Criteria:

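### ICH substudy Aim 1b compares first-CT hematoma volume between early and late scans, but the 60 cc entry limit truncates that same volume and pulls the difference towards zero.

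*Protocol*

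**What the plan says.** All of the relevant text is in Protocol Appendix 4.

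- **Inclusion Criteria, item 2:** "Parenchymal ICH on first CT scan < 60cc". No aim is named. Item 3 does carry a restriction: "At least one SBP reading >150 or INR > 1.4 (only for SA 2". Items 1 and 2 therefore apply to the whole substudy.
- **Aim 1b, entry:** "Patients will be included if they have baseline CT carried out within 4 hours of symptom onset", on the MSU or in the ED. This sentence says nothing about volume.
- **Primary Outcomes, Aim 1, item 2:** the outcome is the "Difference in average hematoma volume on baseline scans between 0-2 hour and 2-4 hour patients (Group 1 or 2" (both study arms contribute).
- **Interpretation:** the same item states that "The difference in average volume will represent the average volume of EHE occurring during the time interval between the two populations". The Aim 1b text says the same of "The difference in average volume between those with baseline scan within 2 hours of symptom onset vs those scanned 2- 4 hours after onset".
- **Sample size, Aim 1b:** mean log volume 2.9 (SD 1.2) at 2-4 hours and 2.0 at 0-2 hours, 32 patients per group, 80% power, two-sided 0.05. Volumes are to be log-transformed and all analyses adjusted for baseline NIHSS, antiplatelet use and comorbidities.

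Appendix 4 gives no truncated-data method and no analysis without the limit, and the sample size makes no allowance for it.

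**The concern.** An entry limit on a baseline variable normally just narrows the population studied. Here the limited variable is the outcome, and Aim 1b expects its distribution to differ between the groups being compared. A bleed that passes 60 cc before a first scan at 2-4 hours is left out. The same bleed scanned earlier, while still below 60 cc, is kept. If the hypothesis is true, the upper tail is cut harder in the late group, so the comparison is biased towards finding little early growth.

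Two things are at stake. The protocol equates the group difference with EHE volume, so the bias passes straight into a reported growth figure. The stated power also refers to untruncated distributions, so a small or null Aim 1b result could be partly a product of the entry rule.

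**Working it through.** **Inputs from Appendix 4.** Limit 60 cc, ln(60) = 4.094. Late group mean 2.9, SD 1.2; early group mean 2.0; 32 per group; two-sided 0.05; 80% power.

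**Assumptions.** Natural logs (on base 10, 2.9 would mean about 790 cc). Normal log volumes. The early group, for which no SD is given, has the same SD. The planning values describe uncapped ICH. The comparison is unadjusted.

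**1. The plan's own figure.** n per group = 2(1.960 + 0.842)² × 1.2² / 0.9² = 27.9, so 28; the t-test version gives 29. The size of the allowance for multivariable analysis is not stated. With an assumed 10%, 29 × 1.1 = 31.9, so 32, as stated. The same 10% reproduces Aim 1a (42 to 47) and Aim 3 (18 to 20).

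**2. Share excluded.** b = (4.094 − μ)/σ; share excluded = 1 − Φ(b).
- Late: b = 1.194/1.2 = 0.995, so 16.0%.
- Early: b = 2.094/1.2 = 1.745, so 4.0%.

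**3. Log difference after the limit.** With λ = φ(b)/Φ(b), the mean is μ − σλ and the SD is σ√(1 − bλ − λ²).
- Late: λ = 0.289, mean 2.9 − 0.347 = 2.553, SD 0.951.
- Early: λ = 0.091, mean 2.0 − 0.109 = 1.891, SD 1.096.
- Difference 0.662 instead of 0.900, which is 26% smaller. Pooled SD = √((0.951² + 1.096²)/2) = 1.026. Simulation gave 0.661.

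**4. Power (two-sample t-test).** The standardized difference falls from 0.900/1.2 = 0.75 to 0.662/1.026 = 0.645.
- At 32 per group: 84% falls to 72%.
- At 29 per group (the number before the allowance): 80% falls to about 67%.
- Regaining 80% needs 39 per group, or 39 × 1.1 = 42.9, so 43 per group (86 in total).

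**5. Mean volume in cc.** Uncapped mean = exp(μ + σ²/2): 37.3 and 15.2, difference 22.2. The capped mean multiplies this by Φ(b − σ)/Φ(b): 18.6 and 11.2, difference 7.4, which is 66% smaller.

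**6. Sensitivity to the SD** (means 2.9 and 2.0):

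| SD | Excluded, late / early | Capped log difference (true 0.90) | Mean cc difference, uncapped to capped |
|---|---|---|---|
| 1.2 | 16.0% / 4.0% | 0.66 (26% smaller) | 22.2 to 7.4 (66% smaller) |
| 1.0 | 11.6% / 1.8% | 0.72 (20% smaller) | 17.8 to 8.9 (50% smaller) |
| 0.8 | 6.8% / 0.4% | 0.80 (11% smaller) | 14.9 to 10.4 (30% smaller) |

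**7. Sensitivity to the true difference** (late mean 2.9, SD 1.2; formula of step 3):

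| True log difference | Capped | Absolute loss | Proportional loss |
|---|---|---|---|
| 0.20 | 0.131 | 0.069 | 35% |
| 0.90 | 0.662 | 0.238 | 26% |
| 1.50 | 1.192 | 0.308 | 21% |

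Moving the late mean to 2.5 or 3.3 with a true difference of 0.9 gives 0.74 or 0.58. The direction was the same in every case.

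**The case against.** **The four-hour CT sentence might be Aim 1b's real entry rule.** It does not waive item 2, and Aim 2 repeats it, so it is not an exemption peculiar to 1b. If no limit was intended for 1b, the text still has to say so.

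**A 60 cc limit is a legitimate population choice.** It is, and Appendix 7 uses it too. In Aim 1a it restricts who is studied but does not truncate the outcome, which is growth between paired scans of the same patient. The direct natural-history evidence therefore does not depend on Aim 1b. This narrows the point but does not remove it for 1b.

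**The planning values may already come from capped data.** Appendix 4 does not describe their source. A normal distribution cut above at 4.094 with mean 2.9 must have an SD below 4.094 − 2.9 = 1.194, so 1.2 does not fit. That margin is narrow and the check itself assumes normality, so the size of the bias remains conditional.

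**Other filters act first.** The main study does not enroll clinically unstable patients (Protocol 5.C.3 and 5.C.4), and Appendix 4 excludes intraventricular blood filling more than half of the lateral ventricle. If large bleeds are over-represented there, which the documents cannot show, the limit's own effect is below 16% versus 4%. These filters would also remain after the fix.

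**The planned analysis is adjusted.** The figures above are unadjusted; attenuation of the adjusted estimate was not computed.

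A reader might infer that the late group loses precisely the fastest-growing bleeds. The text does not support that. The limit removes the largest bleeds, including those that grew past 60 cc before the scan. A bleed that grows from 5 to 50 cc stays in, and one already above 60 cc on an early scan is also excluded.

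**Conclusion.** The point stands for Aim 1b: the entry limit truncates the aim's own outcome, and under its hypothesis the bias is towards zero. The direction holds for any common shift of a normal distribution on the log scale. The size rests on the assumptions listed: a log difference 26% smaller with the protocol's SD of 1.2 (20% at SD 1.0, 11% at SD 0.8), and power of 72% instead of 84% at 32 per group. The cc figure, 30% to 66% smaller over the same SDs, depends heavily on the upper tail and should be given only as a range; the planned analysis is on the log scale.

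A reader might also infer that the bias becomes proportionally worse as true early growth increases. With the late mean fixed at the protocol's 2.9, the absolute loss rises but the proportional loss falls, from 35% to 21% in step 7. The proportion rises only if the early mean is held fixed instead. Nor does the point extend to Aim 1a's outcome or to the trial's primary outcome. It should be corrected, at the weight due to one aim of a substudy.

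**What to change.** In Appendix 4:

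1. State that, for analysis, inclusion item 2 applies to Aims 1a, 2 and 3 only.
2. Analyse Aim 1b on the log scale already planned, in all enrolled patients with parenchymal ICH on a first CT within 4 hours, whatever the volume.
3. Report the under-60 cc subset as a sensitivity analysis, with the number of patients at or above 60 cc in each time group.
4. Replace the statement that the difference represents EHE volume, in both places, with an estimate subject to the remaining selection on severity (clinical instability, intraventricular blood).

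If the limit is kept for Aim 1b, delete the sentences equating the difference with EHE volume, call it a truncated comparison and restate its power.

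The cost is a few sentences and volume measurement on some additional first CTs. Those scans are already acquired, and hematoma volume on all scans is already a listed variable for both groups. Very large bleeds would widen the spread of raw volumes, which the log scale largely handles. No treatment changes.
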